5.3. Study procedure

Upon the obtainment of local Institutional Review Board/Ethical Committee (IRB/EC) approval, each center will choose a start date and the screening process will take place. The local investigator will supervise and coordinate the screening and enrollment procedures in the local center.

5.4. Withdrawal of individual subjects

Subjects can leave the study at any time for any reason if they wish to do so without any consequences.

5.5. Replacement of individual subjects after withdrawal

There will be no replacement of an individual subject after withdrawal.

5.6. Follow-up of subjects withdrawn from treatment

There will be no follow-up of a subject after withdrawal.

5.7. Premature termination of the study

There will be no reason for premature termination as no research related interventions will take place.

6. STATISTICAL ANALYSIS

The demographic and baseline characteristics of the study population will be reported. Continuous variables will be summarized using median and interquartile range (IQR), and categorical variables will be summarized using frequencies and percentages. The comparison among groups for categorical variables will be performed by considering the Chi-square test or Fisher's exact test whatever is appropriate; for continuous variables, the Wilcoxon -Rank Sum test will be used.

The primary endpoint, namely, the PPCs rate, will be calculated together with the 95% confidence interval (CI). Moreover, the impact of the patient's characteristics on the risk of PPCs will be handled by using appropriate statistical models, such as Logistic Regression. These analyses will be adjusted for potential confounders identified at the study's outset, providing insights into factors that may influence PPCs rates among the patients population subjected to surgery. The 95% CIs on the model OR (Odds Ratios) and predicted probability of PPCs, according to the patient's profile, will be estimated. Handling of missing data will be addressed through robust methods like multiple imputation or complete case analysis, depending on the nature and extent of the missingness. Sensitivity analyses will further assess the robustness of the findings, examining how different assumptions about the missing data and analytical methods influence the results.

The significance of differences will be defined by the p-values, with a value of less than 0.05 considered statistically significant.

The following planned secondary analyses will be performed:

- Cardiac vs non-cardiac surgery
- Elective vs non-elective procedures
- Obese vs non-obese patients
- Open vs minimally invasive/robotic surgery

- Comparison among the different obesity classes
- Practice of weaning from invasive mechanical ventilation
- Impact of geo-economical difference

The analyses will be performed by using R 3.4.2.

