2.2. Study objectives

- To describe the incidence and type of PPCs in the first 5 postoperative days;
- To describe associations of patient, surgery, and intraoperative ventilation characteristics with the occurrence of PPCs;
- To describe the impact of intraoperative hemodynamic management on the occurrence of PPCs;
- To describe the occurrence of intraoperative adverse events (IAEs); and
- To describe geo
 economic differences in intraoperative ventilation management.

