3. STUDY DESIGN

This is an observational investigator-initiated, international, multicenter, prospective, cross-sectional study recruiting academic and non-academic centers.

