3.2. Study duration

The overall duration of the study is 18 months, with 9 months allocated for enrollment and data collection, and 9 months dedicated to statistical analysis. Participating hospitals have to prospectively collect data in a consecutive manner within a predefined period of 1 week. Participating hospitals can decide on which period they choose to collect data, but data collection must take place during a predetermined time window of 8 weeks.

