4.4. Sample size calculation

The sample size estimation for the multicenter data-registry was carried out focusing on the main outcome, the PPCs rate of incidence among patients subjected to IMV during general anesthesia for surgery. Initial results presented in existing research highlighted an event rate around 10% (4); Figure 1 was used to determine the size of the study through a method focused on optimizing the precision of the estimates in terms of Confidence Interval (CI) width. The calculation indicates that a sample size of 10,000 subjects will achieve a confidence interval width of 0.0119, as shown in Figure 1. The Clopper-Pearson method was employed for this estimation process, as a more conservative solution.

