5.2. Data collection

Hospitals participating in the study will proactively gather data from all surgical procedures involving patients in a consecutive manner, under the supervision of the local investigator. All data collected are integral to standard clinical care. A visual representation of the trial's design can be found in Figure 2.

Patient characteristics: information such as baseline characteristics and preoperative risk factors essential for identifying patients prone to PPCs. This includes details like age, gender, height, weight, predicted body weight, smoking status, comorbidities, preoperative biochemical exams, peripheral oxygen saturation (SpO2), frailty scale, and American Society of Anesthesiologists (ASA) score. Additionally, data on the type and indication for surgery will be gathered for computing the Assess Respiratory Risk in Surgical Patients in Catalonia (ARISCAT) and Revised Cardiac Risk Index (RCRI). Surgical characteristics: urgency degree of surgery (emergent vs urgent vs elective procedure), planned duration of surgery, type of surgical procedure, and surgical technique.

Operator characteristics: gender, years of anesthesiologist practice, and experience in critical care.

Center characteristics: academic vs non-academic, grade of workload.

Data collection on day 0: type of anesthesia (volatile anesthetic medications or intravenous agents); IMV settings and monitored parameters will be intra-operatively collected at induction and hourly including ventilatory mode, peak inspiratory pressure (cmH₂O), plateau pressure (cmH₂O) (if available), inspiratory to expiratory ratio (I/E), and plateau time (seconds or %), mean airway pressure (cmH₂O), actual inspired tidal volume (Vt) (ml), applied positive end-expiratory pressure (PEEP) and total PEEP with any intrinsic PEEP (cmH₂O) (if present), respiratory rate (breaths/min), dynamic and static respiratory system compliance (cmH₂O/ml) (if clinically available); airway

resistance (Raw) (cmH₂O/(l/sec)) (if clinically available), inspired oxygen fraction (FiO₂), use of recruitment maneuvers (number and type), peripheral oxygen saturation (SpO₂) (%), end-tidal carbon dioxide tension (EtCO₂) (mmHg or kPa), mean, systolic, and diastolic arterial pressure (either invasive or non-invasive) (mmHg), heart rate (beats per minute), body temperature (°C) (if assessed), and arterial blood gases analysis (if present).

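### The group tests named in Section 6 assume independent patients, so the planned geo-economic comparison, which is made between whole centres, would run at several times its nominal 5% error

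*Protocol*

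**What the plan says.** Section 3 describes the study as "international, multicenter, prospective, cross-sectional study recruiting academic and non-academic centers". Section 3.2 sets the sampling: "Participating hospitals have to prospectively collect data in a consecutive manner within a predefined period of 1 week". Patients therefore come in blocks by hospital.

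Section 6 names the group tests without qualification: "The comparison among groups for categorical variables will be performed by considering the Chi-square test" or Fisher's exact test, and "for continuous variables, the Wilcoxon -Rank Sum test will be used". The threshold is p below 0.05. The Summary names tests of the same kind (t-test or Mann-Whitney, chi-square or Fisher).

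Section 6 lists seven planned secondary analyses, one of them the effect of geo-economic difference. Section 2.2 makes this an objective, namely to describe geo-"economic differences in intraoperative ventilation management". Section 5.2 also collects "Center characteristics: academic vs non-academic, grade of workload", but no comparison by these is listed.

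For associations with PPCs, Section 6 calls for appropriate models and gives logistic regression as an example, adjusted for confounders that are still to be identified. Neither centre nor country appears anywhere in the analysis text: no random effect, GEE, robust variance or stratification.

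**The concern.** Chi-square, Fisher and Wilcoxon tests take each patient as a separate piece of information. A hospital belongs to one country and so to one geo-economic group. The evidence on geo-economic difference therefore comes mainly from the number of hospitals and countries, not from the 10,000 patients. If patients in the same hospital resemble each other in PPC rate or in how they are ventilated, the named tests use too small a standard error.

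At stake is a stated objective. Differences in ventilation practice or PPC rate between geo-economic groups could be declared significant when they are no larger than ordinary variation between hospitals.

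**Working it through.** **Inputs from the protocol.** N = 10,000 and a 95% interval width of 0.0119 (Section 4.4: "a sample size of 10,000 subjects will achieve a confidence interval width of 0.0119"); PPC rate 10% (Section 4.4: "Initial results presented in existing research highlighted an event rate around 10% (4"); significance level 0.05 (Section 6), taken as two-sided because sidedness is not stated.

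**Inputs assumed.** Patients per centre, m: 50 or 100, hence 10,000/50 = 200 or 10,000/100 = 100 centres. ICC for PPC: 0.01 to 0.05. ICC for a ventilator setting: 0.05 to 0.2. The documents give none of these.

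**Step 1: the plan's own figure.** Clopper-Pearson limits for 1,000/10,000 are 0.09419 and 0.10605, a width of 0.01186, which rounds to the stated 0.0119. The figure reproduces, but it too treats patients as independent.

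**Step 2: PPC compared between groups of centres.** The design effect is DE = 1 + (m − 1) × ICC. The true error of a nominal two-sided 5% test is 2 × [1 − Φ(1.96/√DE)]. For m = 50 and ICC 0.01: DE = 1 + 49 × 0.01 = 1.49, 1.96/√1.49 = 1.606, error 0.108. The simulation draws centre rates from a beta distribution, places half the centres in each group, sets no true difference and uses 4,000 runs per setting.

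| m | ICC | DE | Error, formula | Error, simulated |
|---|---|---|---|---|
| 50 | 0.01 | 1.49 | 0.108 | 0.111 |
| 50 | 0.02 | 1.98 | 0.164 | 0.153 |
| 50 | 0.05 | 3.45 | 0.291 | 0.285 |
| 100 | 0.01 | 1.99 | 0.165 | 0.172 |
| 100 | 0.02 | 2.98 | 0.256 | 0.267 |
| 100 | 0.05 | 5.95 | 0.422 | 0.422 |

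**Step 3: a ventilator setting compared between groups of centres.** This is the objective in Section 2.2. With m = 50 and ICC 0.2, DE = 1 + 49 × 0.2 = 10.8, 1.96/√10.8 = 0.596, error 0.55. At ICC 0.05, DE = 3.45 and the error is 0.29. Simulating the Wilcoxon test on a discrete, PEEP-like variable with 200 centres of 50 gave rejection rates of 30%, 41% and 54% at ICC 0.05, 0.1 and 0.2. A separate 1,000-run check gave 27%, 40% and 51%.

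**Step 4: where the problem fades.** The PPC simulation was repeated with other kinds of exposure.
- Exposure balanced within every centre: rejection 0.043 to 0.050, so no inflation.
- Exposure whose prevalence varies by centre (assumed exposure ICC 0.3): 0.070 to 0.149 at m = 50 and 0.083 to 0.201 at m = 100.

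For an exposure with ICC 0.2, the approximation DE = 1 + (m − 1) × ICC of exposure × ICC of outcome gives, for PPC ICC 0.01 to 0.05:
- m = 50: 1 + 49 × 0.2 × 0.01 = 1.10 to 1 + 49 × 0.2 × 0.05 = 1.49, error about 0.06 to 0.11.
- m = 100: DE 1.20 to 1.99, error about 0.07 to 0.17.

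All these figures treat centres as independent of one another. Correlation between centres in the same country would add to the error of a geo-economic contrast.

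**The case against.** The strongest reply is that this is a descriptive registry. Its primary endpoint is a PPC rate with a confidence interval, the geo-economic objective is worded as description, and clustering is a matter that a protocol may leave to an analysis plan. Every ICC and centre count above is also assumed. Part of this stands: the geo-economic question is secondary, and the size of the error is a range. But Section 6 is not silent. It names specific tests and a significance threshold, and those tests do not fit a between-centre contrast.

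Three stronger readings are tempting and should not be drawn.
- A reader might infer that the PPC model is a single-level logistic regression with centre-confounded odds ratios. The text offers logistic regression only as an example and leaves the confounders open, so a centre effect is unspecified, not excluded. Centre confounding would need both exposure and PPC risk to vary by centre after adjustment. That is plausible, since PPCs are taken from charts and depend partly on local use of imaging and respiratory support, but the documents do not show it.
- A reader might infer that all the group p-values are invalid. Only one of the seven listed analyses is purely between centres. Surgery type, urgency and obesity can vary within a centre, and Step 4 shows no inflation when they are balanced there.
- A reader might carry the 55% over to associations between ventilator settings and PPCs. It applies only when the setting is the outcome of a between-centre comparison.

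**Conclusion.** The point holds for the geo-economic comparison and for any other contrast between whole centres. If the tests named in Section 6 are used there, a nominal 5% test has a true error of about 11% to 42% for PPCs (ICC 0.01 to 0.05, 50 to 100 patients per centre). For a ventilator setting as outcome it is about 55% (ICC 0.2, 50 patients per centre). These sizes rest on assumed ICCs and centre sizes. The direction does not depend on the exact values: any positive ICC with more than one patient per centre understates the uncertainty.

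For the PPC association model the defect is smaller: the plan leaves the handling of centre open where it should state it.

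**What to change.** In Section 6:

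1. For geo-economic and any other between-centre contrasts, replace the raw chi-square, Fisher and Wilcoxon tests with mixed-effects models (random intercept for centre, country as a further level where feasible), or with GEE or cluster-robust variance. Base the degrees of freedom on the number of centres or countries.
2. State that the logistic model for PPCs includes a centre random effect or uses centre-robust standard errors.
3. Optionally, enter ventilator settings as the centre mean plus the patient's deviation from it, so that within-centre and between-centre associations are reported separately.

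The analysis file must identify the centre of each patient. The protocol mentions only a patient code, so this should be confirmed. The cost is a change of wording, modest programming and wider intervals. No extra patients or procedures are needed.

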7. ETHICAL CONSIDERATIONS

7.1. Regulation statement

The study will be conducted according to the principles of the Declaration of Helsinki.

7.2. Ethical and Regulatory authorities' approval

All participating centers must submit the study to the local IRB/EC for ethical judgment and obtain document of proof that the trial has been subject to IRB/EC review and given approval/favorable opinion. Considering that all study data is recorded from medical charts and no additional data collection or patient assessment is performed, ethical approval may not be required in some centers. However, where ethical approval is required, this approval must be obtained before the start of inclusion. If authorization/approval/notification by the regulatory authorities is applicable locally, this document should be obtained prior to initiation of the trial in compliance with the applicable regulatory requirement(s).

7.3. Recruitment and consent

The investigator will enroll patients in the study. All adult patients admitted to the operating room and receiving IMV will be included. If needed, informed consent by the patient will be obtained by the investigator.

7.4. Benefits and risks assessment, group relatedness

This study does not result in any risk or burdens to patients.

7.5. Compensation for injury

Since the study only collects data and no research related interventions will take place, participating in the study is without risk.

7.6. Incentives

There is no financial incentive for subjects to participate in this study.

8. ADMINISTRATIVE ASPECTS, MONITORING, AND PUBLICATION

8.1. Handling and storage of data and documents

Local investigators are expected to collect data in an electronic Case Report Form (eCRF), Research electronic data capture – REDCAP). Each local investigator will be trained on the use of eCRF and will receive a personalized account with

username and password. The passwords will only be given to directly involved investigators.

The eCRF will generate a code for patient identification and no patient's name and birth date will be reported in paper and electronic CRF. Any handling of personal data will comply with the General Data Protection Regulation.

Data will be confidentially managed and paper CRFs will be securely stored at each local site. Any information allowing to link a record to a specific patient will be destroyed at the end of the monitoring stage.

8.2. Monitoring and Quality Assurance

In order to minimize the number of errors and missing data we will use standard operating procedures. Accuracy and consistency checks will be carried out through an ad hoc checking by investigation coordinators.

8.3. Public disclosure and publication policy

The study protocol will be registered on www.clinicaltrials.gov before the start of the investigation. The results of the study will be published in international scientific peer-reviewed journals. The project leader will have final responsibility for the decision to submit for publication.

9. PUBLICATION AND AUTHORSHIP POLICY

The main results of the study will be submitted for peer–review and publication to international medical journal. The first report that comes will be written by the Writing Committee, a subgroup of the Steering Commitee; The primary manuscript reporting the study results will have the intention to be published as a paper by the MEET VENUS study group – this may mean that there are no names of individual researchers in the author's byline. The Principal Investigator will be mentioned as the contact person, whereas the members of the Steering Committee, Writing Committee, and ALL national and local investigators of participating centers are summarized at the end of a manuscript or in the appendix depending on the journal policy.

10. PROPOSAL OF SUB-STUDY/ANALYSIS

On request, the dataset will be available for investigators for secondary analyses, after submission of a sub-study/analysis proposal which will be evaluated for approval by the steering committee.

Before submission, the final version of all manuscripts related to the MEET VENUS study dataset must be approved by the Steering Committee. All the publications derived from the MEET VENUS study dataset will be submitted with the investigators

having their names in the authors' byline, but always using 'on behalf of the MEET VENUS study group investigators'.

11. DEFINITIONS

11.1. PPCs definition

For PPCs (within a time window ranging from day of surgery to 5 days after surgery) we intend unplanned supplementary oxygen administration for hypoxemia, i.e., as oxygen saturation less than 90% in room air, but excluding oxygen supplementation given as standard care, e.g. directly after arrival in the post-anesthesia care unit, respiratory failure defined as oxygen saturation less than 90% despite oxygen therapy or need for non-invasive respiratory support (NIRS), unplanned new or prolonged IMV (after discharge from the operating room), acute respiratory distress syndrome (ARDS) (25), pneumonia (presence of a new or progressive radiographic infiltrate and at least two of three clinical features; fever >38°C, leucocytosis, or leukopenia (white blood cells count >12000 cells*µl-3 or <4000 cells*µl-3 and purulent secretions), pneumothorax, pneumomediastinum, and atelectasis (all confirmed through chest radiograph, computed tomography and/or thoracic ultrasonography).For NIRS we intend high flow oxygen therapy, continuous positive airway pressure, and non-invasive bilevel positive airway pressure ventilation.

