4.3. Exclusion criteria

The following patients will be excluded:

- subjected to IMV outside of an operating room; and
- subjected to IMV during extracorporeal life support.

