Weaning phase: at beginning and at the end of weaning phase, the following variables will be acquired: ventilatory mode, Vt (ml), PEEP (cmH₂O), pressure support over PEEP (if any) (cmH₂O), inspiratory trigger regulations, FiO₂, respiratory rate (breaths/min), SpO₂ (%), EtCO₂(mmHg or kPa), mean, systolic, and diastolic arterial pressure (either invasive or non-invasive), mmHg, heart rate (beats per minute).

It will also be recorded if aspiration is performed prior to tube removal. The number and type of IAEs will be acquired throughout the whole duration of surgical and anesthesiologic procedures (see "11" for definitions).

Peri-operative variables: duration of anesthesia procedure, duration of surgical procedure, tube type and size, type of anesthesia, type of analgesia (total endovenous, antibiotic prophylaxis, details on neuromuscular function monitoring and about the use of reversal agents (if any), total intra-operative fluid and total transfusion of blood products, temperature and hemoglobin at end of surgery (if clinically available). The possible admission to post-anesthesia care unit (PACU) and the eventual administration of non-invasive respiratory support (NIRS), namely, high flow oxygen therapy, continuous positive airway pressure, and non-invasive bilevel positive airway pressure ventilation, and the settings will be recorded.

Post-operative variables: vital signs involving SpO₂, heart rate, systolic, diastolic, and mean arterial pressure, body temperature if assessed, eventual arrythmias occurrence, and the blood gas analysis parameters (optional assessment) will be hourly collected in the immediate post-operative period or PACU stay, and at the discharge to surgical ward or ICU.

Follow up (day 0 to 5): PPCs are recorded from the medical chart on day 0 (end of surgery to 23:59h) and on days 1,2,3,4 and 5 post-operative (each day runs from 00:00 AM to 23:59 PM). Follow–up is completed on the day of discharge or on day 5 if the patient is still admitted.

On day 0 the following variables are collected: IMV after discharge from the operation room, admission to ICU/PACU after surgery, PPCs (see "11").

On day 1,2,3,4 and 5 the following variables will be collected: any new admission to ICU; any new or prolonged IMV; PPCs (see "11").

The data mentioned above are considered essential to defined as "complete" each patient's medical record.

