ICU or PACU admission: recording of data during the critical care submission can be left out by the participating centers if this workload exceeds their possibilities. However, it is requested to collect the ICU/PACU data. In case of IMV and/or admission to the ICU/PACU during the follow-up period (day 0, 1, 2, 3, 4 or 5), the following variables will be collected on a different CRF: reason for ICU/PACU admission, reason for IMV or NIRS, APACHE II score (24), on (first) admission to and within the first 24 hours in ICU (i.e., the APACHE II score to be collected and reported for patients who were in the ICU before surgery, and were referred to the ICU after surgery, starts direct after the first admission to the ICU; the APACHE II score to be collected and reported for patients who were not in the ICU before surgery, but were referred to the ICU after surgery, starts direct after surgery, in the ICU). At the first hour of ICU/PACU admission and in case of continued admission each day (during morning rounds) the following variables are collected: SOFA score, IMV regulations, arterial blood gas values (pH, PaCO₂, PaO₂ if available), closest to 08:00 AM, PPCs (number and type, see "p 11"), extra-pulmonary organ failure (number and type), and risk factors for respiratory failure (number and type).

If a patient is transferred back to the ward, the non–ICU/PACU follow–up CRF will be used to record the variables of the remaining follow–up days.

Follow up (day 28): On day 28 ICU and hospital length of stay as well as in hospital death are assessed.

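### The PPC definition does not exclude planned NIRS and does not require pneumothorax, pneumomediastinum or atelectasis to be new, so centres can score the primary endpoint differently

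*Protocol*

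**What the plan says.** Protocol section 11.1 lists the components of the composite, and section 5.1.1 makes their joint incidence the primary endpoint. The components carry different qualifiers:

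- Oxygen: must be unplanned and given for hypoxemia; oxygen given as standard care is excluded.
- Respiratory failure: "respiratory failure defined as oxygen saturation less than 90% despite oxygen therapy or need for non-invasive respiratory support (NIRS". NIRS covers high-flow oxygen, CPAP and bilevel ventilation.
- Invasive ventilation: must be unplanned, and new or prolonged, after leaving the operating room.
- Pneumonia: needs a new or progressive infiltrate plus clinical features.
- Pneumothorax, pneumomediastinum, atelectasis: need confirmation by radiograph, CT or ultrasound.

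Section 5.2 lists among the perioperative variables "the eventual administration of non-invasive respiratory support (NIRS" and its settings. The reason for NIRS appears only on the separate ICU/PACU form, which is requested but which centres may leave out if the workload is too high. Section 5.2 also provides for "patients who were in the ICU before surgery, and were referred to the ICU after surgery", so patients with preoperative critical illness are expected in the cohort.

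Section 4.4 sizes the study on precision: "a sample size of 10,000 subjects will achieve a confidence interval width of 0.0119".

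**The concern.** The authors use *unplanned* and *new* where they want them: for oxygen, ventilation and pneumonia in section 11.1, and for recruitment maneuvers and arrhythmias in section 11.2. A centre may fairly take their absence elsewhere as deliberate. As written, low-flow oxygen given routinely on arrival in the PACU is not a PPC, while nothing says the same of high-flow oxygen given routinely in the same place. The same gap covers a planned post-extubation NIRS protocol or home CPAP continued after surgery. A pneumothorax or atelectasis already present before surgery can appear in the day 0 chart and meet the imaging criterion.

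At stake is the primary rate itself and its comparability between centres. If planned NIRS is used at different frequencies in different groups, the planned contrasts, such as "Obese vs non-obese patients", cardiac versus non-cardiac surgery and the geo-economic comparison, would partly reflect how support is given and charted.

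**Working it through.** **Step 1: compare the components.**

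| Component | Limited to unplanned use? | Must be new? |
|---|---|---|
| Supplementary oxygen | Yes, standard care excluded | Not stated |
| Need for NIRS | Not stated | Not stated |
| Invasive ventilation | Yes | New or prolonged |
| Pneumonia | Not applicable | New or progressive infiltrate |
| Pneumothorax, pneumomediastinum, atelectasis | Not applicable | Not stated |

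Read naturally, the two arms of respiratory failure are alternatives, so need for NIRS establishes the component alone. No threshold or indication defines need.

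**Step 2: can the listed data separate the cases later?** The baseline items in section 5.2 include comorbidities and SpO2 but name no preoperative NIRS, ventilation or imaging status. PACU NIRS is recorded with its settings, with no planned/unplanned item. The ward items for days 1 to 5 include no reason for NIRS. The ICU/PACU form has the reason but may be omitted. Section 8.1 provides for destroying the patient link after monitoring, which ends any return to the charts. Separation would therefore be incomplete.

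**Step 3: reproduce the plan's figure.** Inputs from section 4.4 and Figure 1: rate 10%, n = 10,000, 95% confidence, and "The Clopper-Pearson method was employed for this estimation process, as a more conservative solution". With x = 1,000:

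- lower limit = Beta quantile(0.025; x, n − x + 1) = 0.09419
- upper limit = Beta quantile(0.975; x + 1, n − x) = 0.10605
- width = 0.10605 − 0.09419 = 0.01186, which rounds to the stated 0.0119
- half-width = 0.01186 / 2 = 0.0059

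**Step 4: how much misclassification equals that half-width?** Let the true rate be 10% and let a share f of PPC-free patients be scored wrongly. Then observed rate = 0.10 + 0.90 f. Setting 0.90 f = 0.00593 gives f = 0.0066, that is 0.0066 × 9,000 ≈ 59 patients.

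**Step 5: range of f.** These values of f are assumptions; the documents give none.

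| f | Patients wrongly scored, of 9,000 | Observed rate | 95% CI |
|---|---|---|---|
| 0.5% | 45 | 10.45% | 9.86 to 11.07% |
| 0.66% | about 59 | 10.59% | 9.99 to 11.21% |
| 1% | 90 | 10.90% | 10.30 to 11.53% |
| 2% | 180 | 11.80% | 11.17 to 12.45% |
| 5% | 450 | 14.50% | 13.82 to 15.21% |

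From f = 1% upwards in this table the interval no longer contains the true 10%.

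**The case against.** The strongest reply is that the text, read in context, already points the right way. NIRS counts only as a need, under the label respiratory failure, and prophylactic or home CPAP is not naturally that. Section 5.1.1 counts postoperative complications that occur in the first five postoperative days, which suggests onset after surgery for every component. Individual components will be reported, so an unusual respiratory-failure count would be visible, and the reason for NIRS is collected on the ICU/PACU form.

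Much of this stands as a limit on what can be claimed. A reader might infer that any NIRS counts, or that pre-existing disease is scored as a complication. The documents do not say so; they leave both cases open. The reply does not close the gap, because need is undefined, no component rule or baseline comparison enforces onset, and the reason field is optional and absent from ward follow-up.

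Three further inferences fail:

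- **ARDS.** It is acute by name, rests on a cited definition that cannot be checked here, and stands outside the imaging clause. It should not be grouped with the three imaging components.
- **Section 4.3.** The exclusion of patients "subjected to IMV outside of an operating room" could be read as removing those who meet the postoperative ventilation component. That reading is strained, since sections 5.2 and 11.1 expressly collect and count ventilation after the operating room, and it concerns eligibility rather than the PPC definition.
- **A quantified bias in the obesity contrast.** This would need an obesity share, PPC rates by group and planned-NIRS rates in both groups. The documents give none of these.

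**Conclusion.** The point holds as an inconsistency in the primary endpoint definition. Centres can score planned, prophylactic or continued home NIRS, and imaging findings present before surgery, as PPCs, and the listed data would not fully allow this to be undone. Scoring such cases can only raise the rate. Neither the size of the inflation nor the direction of any difference between groups can be derived from the documents.

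The 0.66% figure is a yardstick, not an estimate. It assumes a true rate of 10%, 10,000 analysed patients, and errors only among patients with no other PPC. It shows that the planned precision is fine enough for a small scoring difference to matter. The plan's own width of 0.0119 is correct and is not in dispute. This is an inexpensive improvement worth making before data capture; the design remains sound without it.

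**What to change.** 1. In section 11.1, word the NIRS component as unplanned NIRS for respiratory deterioration, excluding planned or prophylactic NIRS and continuation of preoperative NIRS.
2. In the same section, add *new (not present before surgery)* to pneumothorax, pneumomediastinum and atelectasis.
3. On the core eCRF, not the optional ICU/PACU form, add a planned yes/no flag for NIRS and preoperative respiratory-support status.
4. Report the primary rate with all NIRS counted as a sensitivity analysis.

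The cost is a change of definition wording, a few extra fields per patient, a slightly lower PPC rate, and less direct comparability with sources that count all NIRS. The sensitivity analysis covers the last of these. No patient's care changes.
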